Appendix 6: Drug accountability form

Original: monitor
 1st copy: investigator/pharmacist

Drug : VINFLUNINE	Protocol No : L00070 IN 309 F0	Page 1 / 1
Subject No _ _ _ _ _ _ _ _ _	Subject's Drug Accountability Form	

A PHASE III TRIAL OF IV VINFLUNINE IN COMBINATION WITH METHOTREXATE VERSUS METHOTREXATE ALONE IN PATIENTS WITH RECURRENT OR METASTATIC SQUAMOUS CELL CARCINOMA OF THE HEAD AND NECK PREVIOUSLY TREATED WITH PLATINUM-BASED THERAPY

ARM A

CYCLE N° : |_|_| **DATE OF DISPENSATION :** |_|_| |_|_| |_|_|_|_|

• **VINFLUNINE**

Dispenser's Initials	Dose level (mg/m ²)	Dose dispensed (mg)	Number of vials 50 mg / 2 mL	Number of vials 250 mg / 10 mL	Date control CRA
	_ _ _ _	_ _ _ _	_ _ _	_ _ _	

When possible, please use the vials **in chronological order** and stick here the labels.

Comments : _____

Date : |_|_|_| |_|_|_| |_|_|_|_|_|

INVESTIGATOR/PHARMACIST:

Name : _____ *Signature :* _____

C.R.A.:

Name : _____ *Signature :* _____

- Original: monitor
- 1st copy: investigator/pharmacist

Drug : VINFLUNINE	Protocol No : L00070 IN 309 F0	Page 1 / 1
Subject No _ _ _ _ _ _ _ _ _	Subject's Drug Accountability Form	

A PHASE III TRIAL OF IV VINFLUNINE IN COMBINATION WITH METHOTREXATE VERSUS METHOTREXATE ALONE IN PATIENTS WITH RECURRENT OR METASTATIC SQUAMOUS CELL CARCINOMA OF THE HEAD AND NECK PREVIOUSLY TREATED WITH PLATINUM-BASED THERAPY

ARM A OR B

CYCLE N°: |_|_| **DAY:** |_|_| **DATE OF DISPENSATION :** |_|_| |_|_| |_|_|_|_|

• **METHOTREXATE**

Dispenser's Initials	Dose level (mg/m ²)	Dose dispensed (mg)	Number of vials 50 mg / 2 mL	Date control CRA
	_ _ _ _	_ _ _ _	_ _ _	

When possible, please use the vials **in chronological order** and stick here the labels.

Comments : _____

Date : |_|_|_| |_|_|_| |_|_|_|_|_|_|

INVESTIGATOR/PHARMACIST:

Name : _____ *Signature :* _____

C.R.A.:

Name : _____ *Signature :* _____

Appendix 7: EORTC questionnaire

EORTC QLQ-C30 (version 3)

We are interested in some things about you and your health. Please answer all of the questions yourself by circling the number that best applies to you. There are no "right" or "wrong" answers. The information that you provide will remain strictly confidential.

Please fill in your initials:

|_|_|_|_|_|_|_|

Your birthdate (Day, Month, Year):

|_|_|_|_|_|_|_|_|_|_|_|_|_|_|_|_|_|

Today's date (Day, Month, Year):

31 |_|_|_|_|_|_|_|_|_|_|_|_|_|_|_|_|_|

	Not at All	A Little	Quite a Bit	Very Much
1. Do you have any trouble doing strenuous activities, like carrying a heavy shopping bag or a suitcase?	1	2	3	4
2. Do you have any trouble taking a long walk?	1	2	3	4
3. Do you have any trouble taking a short walk outside of the house?	1	2	3	4
4. Do you need to stay in bed or a chair during the day?	1	2	3	4
5. Do you need help with eating, dressing, washing yourself or using the toilet?	1	2	3	4
During the past week	Not at All	A Little	Quite a Bit	Very Much
6. Were you limited in doing either your work or other daily activities?	1	2	3	4
7. Were you limited in pursuing your hobbies or other leisure time activities?	1	2	3	4
8. Were you short of breath?	1	2	3	4
9. Have you had pain?	1	2	3	4
10. Did you need to rest?	1	2	3	4
11. Have you had trouble sleeping?	1	2	3	4
12. Have you felt weak?	1	2	3	4
13. Have you lacked appetite?	1	2	3	4
14. Have you felt nauseated?	1	2	3	4
15. Have you vomited?	1	2	3	4
16. Have you been constipated?	1	2	3	4

Please go on to the next page

During the past week

	Not at All	A Little	Quite a Bit	Very Much
17. Have you had diarrhea?	1	2	3	4
18. Were you tired?	1	2	3	4
19. Did pain interfere with your daily activities?	1	2	3	4
20. Have you had difficulty in concentrating on things, like reading a newspaper or watching television?	1	2	3	4
21. Did you feel tense?	1	2	3	4
22. Did you worry?	1	2	3	4
23. Did you feel irritable?	1	2	3	4
24. Did you feel depressed?	1	2	3	4
25. Have you had difficulty remembering things?	1	2	3	4
26. Has your physical condition or medical treatment interfered with your family life?	1	2	3	4
27. Has your physical condition or medical treatment interfered with your social activities?	1	2	3	4
28. Has your physical condition or medical treatment caused you financial difficulties?	1	2	3	4

For the following questions please circle the number between 1 and 7 that best applies to you

29. How would you rate your overall health during the past week?

1 2 3 4 5 6 7

Very poor

Excellent

30. How would you rate your overall quality of life during the past week?

1 2 3 4 5 6 7

Very poor

Excellent

EORTC QLQ - H&N35

Patients sometimes report that they have the following symptoms or problems. Please indicate the extent to which you have experienced these symptoms or problems during the past week. Please answer by circling the number that best applies to you.

During the past week:

	Not at all	A little	Quite a bit	Very much
31. Have you had pain in your mouth?	1	2	3	4
32. Have you had pain in your jaw?	1	2	3	4
33. Have you had soreness in your mouth?	1	2	3	4
34. Have you had a painful throat?	1	2	3	4
35. Have you had problems swallowing liquids?	1	2	3	4
36. Have you had problems swallowing pureed food?	1	2	3	4
37. Have you had problems swallowing solid food?	1	2	3	4
38. Have you choked when swallowing?	1	2	3	4
39. Have you had problems with your teeth?	1	2	3	4
40. Have you had problems opening your mouth wide?	1	2	3	4
41. Have you had a dry mouth?	1	2	3	4
42. Have you had sticky saliva?	1	2	3	4
43. Have you had problems with your sense of smell?	1	2	3	4
44. Have you had problems with your sense of taste?	1	2	3	4
45. Have you coughed?	1	2	3	4
46. Have you been hoarse?	1	2	3	4
47. Have you felt ill?	1	2	3	4
48. Has your appearance bothered you?	1	2	3	4

During the past week:

	Not at all	A little	Quite a bit	Very much
49. Have you had trouble eating?	1	2	3	4
50. Have you had trouble eating in front of your family?	1	2	3	4
51. Have you had trouble eating in front of other people?	1	2	3	4
52. Have you had trouble enjoying your meals?	1	2	3	4
53. Have you had trouble talking to other people?	1	2	3	4
54. Have you had trouble talking on the telephone?	1	2	3	4
55. Have you had trouble having social contact with your family?	1	2	3	4
56. Have you had trouble having social contact with friends?	1	2	3	4
57. Have you had trouble going out in public?	1	2	3	4
58. Have you had trouble having physical contact with family or friends?	1	2	3	4
59. Have you felt less interest in sex?	1	2	3	4
60. Have you felt less sexual enjoyment?	1	2	3	4

During the past week:

	No	Yes
61. Have you used pain-killers?	1	2
62. Have you taken any nutritional supplements (excluding vitamins)?	1	2
63. Have you used a feeding tube?	1	2
64. Have you lost weight?	1	2
65. Have you gained weight?	1	2

Appendix 8: Inducers or inhibitors of CYP3A4

Non-exhaustive list of inducers and inhibitors of CYP 3A4

These treatments should be stopped at least 4 days before the 1st drug administration of **the pharmacokinetic study**. However, their topical form is authorised.

They are allowed, if necessary during the **compassionate use** of vinflunine.

Inducers of isoform cytochrome P450 3A4

Millepertuis (Hypericum ; St John's Wort)

Antiepileptic

Barbiturate: Phenobarbital, Primidone

Non barbiturate: Phenytoin, Carbamazepine, Oxcarbazepine

Antiretroviral

Efavirenz, Nevirapine

Antifungal

Griseofulvin

Antimycobacterial

Rifabutin, Rifampicin

Corticosteroid

Dexamethasone

Antihypertensive

Bosentan

Antidepressant

Fluvoxamine

Inhibitors of isoform of cytochrome P450 3A4

Grape fruit juice

Antiretroviral

Amprenavir, Delavirdine, Indinavir, Nelfinavir, Ritonavir, Saquinavir, Atazanavir, Darunavir

Antibacterial

Macrolide: Troleandomycin, Erythromycin, Telithromycin, Clarithromycin

Chloramphenicol

Antimycobacterial

Isoniazid

Antifungal

Triazole: Fluconazole, Itraconazole, Voriconazole

Imidazole: Ketoconazole, Miconazole

Oestrogen

Ethinylestradiol

Androgen

Danazol

Calcium-channel blocker

Diltiazem, Nicardipine, Verapamil

Anti-arrhythmic agent

Amiodarone

Leukotriene antagonist

Zafirlukast

Reference list

[figure not shown]
Hansten P.H, Horn J.R.

The top 100 drug interactions. A guide to patient management, 2007 Edition, H&H Publication

Affsaps

Referenciel national des interactions médicamenteuses – Interactions médicamenteuses et cytochromes, April 2005.

Appendix 9: Diagram of categories of eligible patients according to inclusion criterion no.3

CT = chemotherapy

*** cisplatin + 5-FU or docetaxel + cisplatin + 5-FU**

## LIST OF ABBREVIATIONS AND DEFINITIONS

AEs	Adverse Events
AEOSI	Adverse Events Of Special Interest
ALT	Alanine aminotransferase
ANC	Absolute Neutrophil Count
AST	Aspartate aminotransferase
BSA	Body Surface Area
CI	Confidence Interval
CISH	Chromogenic In Situ Hybridisation
CMH	Cochran-Mantel-Haenszel
CR	Complete Response
CRF	Case Report Form
CSR	Clinical Study Report
CTCAE	Common Terminology Criteria for Adverse Events
DCR	Disease control rate
DI	Dose Intensity
EGFR	Epidermic Growth Factor Receptor.
EORTC	European Organisation for Research and Treatment of Cancer
ER	Estrogen Receptor
FISH	Fluorescent In Situ Hybridisation
FN	Febrile Neutropenia
HB	Haemoglobin
HLGT	High Level Group Term
HLT	High Level Term
HR	Hormone Receptor
i.v.	Intravenous
IDMC	Independent Data Monitoring Committee
IHC	Immunohistochemistry
ITT	Intent-To-Treat
LLT	Lowest Level Term
MedDRA	MEDICAL DICTIONARY FOR REGULATORY ACTIVITIES
MTX	Methotrexate
ORR	Objective Response Rate
OS	Overall Survival
PD	Progression Disease
PDI	Planned Dose Intensity
PgR	Progesterone Receptor
PLT	Platelets

PR	Partial Response
PS	Performance Status
PFS	Progression-Free Survival
PRES	Posterior Reversible Encephalopathy Syndrome
PT	Preferred Term
pt (s)	Patient (s)
QoL	Quality of Life
RDI	Relative Dose Intensity
RECIST	Response Evaluation Criteria In Solid Tumors
SAE(s)	Serious Adverse Event(s)
SAP	Statistical Analysis Plan
SAS	Statistical Analysis Software
SCCHN	Squamous Cell Cracinoma of Head and Neck
SD	Stable Disease
SGOT	Serum Glutamic Oxaloacetic Transaminase
SGPT	Serum Glutamic Pyruvic Transaminase
SIADH	Syndrome of Inappropriate Anti-Diuretic Hormone Secretion
SOC	System Organ Class
TEAE	Treatment Emergent Adverse Event
TTF	Time to Treatment Failure
ULN	Upper Limit of Normal
VFL	Vinflunine
WBC	White Blood Cells
WHO	World Health Organisation
Wk(s)	Week(s)

## 1. STUDY OBJECTIVES

The primary objective of the trial was to compare the overall survival of the i.v. vinflunine in combination with methotrexate versus methotrexate alone in incurable recurrent/metastatic squamous cell carcinoma of the head and neck (SCCHN) patients who have failed platinum-based chemotherapy.

The results of the 2nd interim analysis (August 2015) of efficacy have led the IDMC to recommend the implementation of a futility analysis of overall survival which is the primary endpoint of study 309. This futility analysis was carried out by IDDI, a CRO expert in biostatistics, independently from the sponsor and the results reviewed by the IDMC.

The results of the futility analysis showed that the probability to demonstrate a significant benefit of overall survival at the time of the final analysis is very low.

As a consequence, Pierre Fabre has decided to stop the recruitment of study patients on 16th October 2015.

This SAP is aimed to adapt the statistical analysis according to the protocol amendment 11.

## 2. STUDY DESIGN

This multicentre, open-label, randomized, Phase III study will enrol 530 patients with SCCHN who have failed platinum-based chemotherapy. Patients will be randomised in a 1:1 ratio to receive i.v. vinflunine plus methotrexate (arm A) or methotrexate alone (arm B).

Randomisation will be stratified according to a minimisation procedure (**Pocock SJ, 1975**):

- WHO performance status (0 versus 1)
- Refractory or resistant to platinum versus other
- Prior radiotherapy (yes versus no)
- Prior treatment with any anti-EGFR medication (yes versus no)
- Center

### **Patients will be randomised to receive:**

- Arm A : i.v. vinflunine 280 mg/m^2 on day 1 and methotrexate 30 mg/m^2 on days 1 and 8 every 3 weeks.
- Arm B : methotrexate 40 mg/m^2/week.

Overall survival (OS) will be the primary endpoint of the study. The final analysis will require at least 437 deaths. The study has been powered at 90% to show an improvement of survival from 5.5 months in the control arm to 7.5 months in the test arm.

Throughout the study, patients will be closely monitored for safety evaluation and will be assessed for tumour response every 6 weeks. Patients will receive at least 2 cycles unless they experienced unacceptable toxicity or early disease progression. Patients who respond or have stable disease will

receive 2 additional cycles and will be reevaluated for tumour response. Patients with progressive disease will be removed while patients who respond or have stable disease may continue study treatment until disease progression.

### 3. SAMPLE SIZE

The primary objective of the study was to show that the vinflunine plus methotrexate (arm A) is superior to methotrexate alone (arm B) in terms of overall survival. The final analysis will require at least 437 deaths; this is the number of events needed for a two sided, log-rank test at an alpha = 0.05 significance level to have 90% power to show a statistically significant difference when the true hazard ratio is 0.733 (i.e., when the median OS in the vinflunine arm is 7.5 months and the median OS in the control arm is 5.5 months). An expected total number of 530 patients was planned. It was estimated that the study will take approximately 19 months to accrue and the OS analysis is expected to be performed ten months following the last patient accrued. The anticipated lost to follow-up is estimated to be 5%.

Following the decision to stop the recruitment:

- The statistical analysis will actually be conducted on the 459 randomised patients.
- 325 events should be observed at the end of study allowing a power of 80%.

Whatever the number of events at the end of study, the final analysis of OS (primary analysis) will be performed on the ITT population. Only descriptive analyses will be performed on all secondary efficacy analyses for ITT population.

### 4. EFFICACY PARAMETERS

Tumour assessment will be performed according to the revised RECIST guidelines version 1.1 (Therasse P, 2000, Eisenhauer E, 2009). Assessment of all lesions was planned to be carried out at baseline then every 6 weeks (+/- 3 working days) until disease progression, regardless of the timing of the treatment cycles and whatever the treatment administered.

For patients who discontinued the study treatment before the occurrence of disease progression, clinical and radiological assessments of all lesions had to be performed every 6 weeks from time of randomisation until disease progression is documented, then survival information was collected approximately every month for the first 6 months and then every 3 months until death.

For patient who discontinued the study treatment due to PD, survival information was collected approximately every month for the first 6 months and then every 3 months until death.

According to the protocol amendment 11, no follow-up visit will be performed. At the time of this amendment:

- patients under treatment will stop the study at the EOT
- patients under follow-up will stop immediately

The end of study is defined as the date of the last study treatment plus 30 days for the last patient on treatment (EOT of the last patient).

## 4.1. PRIMARY EFFICACY PARAMETERS

### 4.1.1. Overall survival

The primary efficacy parameter is overall survival defined as the time from randomization to the date of death or last follow-up. For patients who have not died, survival duration will be censored at the date of last contact or last follow-up.

## 4.2. SECONDARY EFFICACY PARAMETERS

The secondary efficacy parameters are:

- The Progression-Free survival in both arms,
- The Objective Response and Disease Control rates in both arms,
- The duration of response, disease control and time to first response in both arms

### 4.2.1. Progression free survival

Progression-free survival will be calculated from the date of randomisation until the date of progression or death (whatever the reason of death). Patients lost to follow-up, or without a known record of progression or death at time of analysis will have the progression-free survival censored at the date of last tumour assessment or the date of last contact of a follow-up showing no progression, whichever occurs last.

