Sensitivity analyses of PFS will be performed in the ITT population and in the eligible population. Firstly, an analysis will be conducted in which patients who did not show evidence of PD before starting new anti cancer therapy will be censored at the date of initiation of new anti-cancer therapy. Secondly, the analysis will be repeated considering the start of new anti-cancer therapy as

an event. These two analyses aim at ruling out the bias that could arrive from the potential imbalance of further anti-cancer therapy between the two arms.

Another sensitive analysis will consider the patient in progression the day after the last tumor assessment showing no progression. For patients who progressed early or were assessed as PD at the first evaluation, they will be considered as progressing at the day after the date of randomisation. This analysis aims at ruling out potential ascertainment bias and taking into account the potential imbalance of early progressors between the two treatment arms.

A multivariate analysis using a stratified Cox proportional hazard model for Progression-Free Survival will be performed on the ITT and Eligible population with the same stratification factors as described above (see §11.5.3.2.1). The following prognostic factors will be taken into account :

- Age (< 50 years versus \geq 50 years),
- Primary tumour site (oral cavity, oropharynx, larynx, hypopharynx, nasal cavity, other),
- Extent of disease (locoregional recurrence versus metastatic disease with or without locoregional recurrence,
- Tumour grade (well or moderately differentiated, poorly differentiated).

In case of missing data in some covariates of the multivariate analysis, in addition of the complete case analysis (listwise selection approach) consisting in omit those cases with missing data and to run the analysis on what remains, a multiple imputation based approach where complete data sets are drawn will be used to perform the multivariate analysis. The imputation model will be defined in the SAP.

11.5.3.2.4.3. Tumour response

The analyses of tumour response will be performed on the ITT population and on the population evaluable for response in the two treatment arms.

❖ Objective Response and Disease Control Rate

Objective Response Rate and Disease Control Rate in each treatment arm will be estimated and presented along with a corresponding 95% confidence interval. The ORR and DCR will be

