#### ***10.4.1.1. Primary analysis of PFS***

The primary analysis of PFS will be done in the ITT. The stratified log-rank test, hazard ratio and 95% confidence interval of the hazard ratio will be computed using the SAS® procedure «PHREG». The treatment arm will be entered as a covariate in the Cox proportional hazard model and the variables of stratification at randomisation (except centre) will be entered as stratification factors in the model.

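### The PFS censoring rule can count time after a missed scan as progression-free, because the last contact need not include a tumour assessment

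*SAP*

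**What the plan says.** SAP 4.2.1 defines PFS from randomisation to progression or death. Patients without either are censored at the last tumour assessment or at "the date of last contact of a follow-up showing no progression, whichever occurs last". Protocol 11.4 has the same rule. SAP 4.2.4 (duration of response) and 4.2.5 (duration of disease control) also take the later of the two dates, but they additionally censor at the start of a new anti-cancer treatment, which SAP 4.2.1 does not.

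Tumour assessment is planned "every 6 weeks (+/- 3 working days) until disease progression" (SAP 4). Under SAP 15.2.3.2, a progression date comes from the Tumour Assessment Form, and a death without earlier progression from the Death Report Form. Since protocol amendment 11 (PA11), "patients under follow-up will stop immediately" (SAP 4).

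Protocol 11.5.3.2.4.2 planned PFS sensitivity analyses, one of them tied to the last scan: "Another sensitive analysis will consider the patient in progression the day after the last tumor assessment showing no progression". SAP 10.4.1 contains none of these. It keeps one analysis, a stratified log-rank test with a Cox hazard ratio: "The primary analysis of PFS will be done in the ITT". SAP 3 gives the status of such results: "Only descriptive analyses will be performed on all secondary efficacy analyses for ITT population".

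**The concern.** Events and censoring rest on different evidence. A progression enters the analysis through the Tumour Assessment Form, but a contact with no tumour assessment can still extend progression-free time. The contact is listed separately from the assessment, so it changes the censoring date only when it falls after the last assessment.

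Such contacts are possible. Protocol 7.7 has survival information collected alongside the six-weekly assessments in patients who stopped treatment before progression. The items listed are the date last known alive, WHO score, details of any death, and later anti-cancer therapy. Tumour status is not among them.

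A patient who misses a scheduled scan but stays in contact remains in the risk set on a date when progression could not be recorded for that patient. The Kaplan-Meier estimate then drops too little at that date. At stake are the PFS curve and medians, the two duration endpoints and, if missed scans differ by arm, the only PFS hazard ratio the SAP reports.

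**Working it through.** **Plan figures.** The plan states no event count, power or censoring assumption for PFS, so there is no figure to reproduce. The 437 and 325 deaths in SAP 3 concern overall survival and are not affected.

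**Inputs from the documents**
- Scan interval 42 days (SAP 4). With the SAP 15.2.1.1 divisor, 42 / 30.4375 = 1.380 months, so scans fall at 1.38, 2.76 and 4.14 months.
- Median PFS 2.0 months, from the best-supportive-care control arm in Protocol Table 2, where 78% received methotrexate. It is borrowed for illustration only.
- 459 patients, allocated 1:1 (SAP 3 and 2).

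**Assumptions without a source**
- Scanning stops at a rate d of 5% or 10% per month, independently of progression.
- Last contact is 2 months after the last scan in every censored patient.
- Event times are exponential and are dated at the next scan.

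**Step 1: correct value at 3 months.** The hazard is ln 2 / 2.0 = 0.3466 per month. The chance of passing one scan interval progression-free is exp(-0.3466 × 1.380) = 0.6199, so 0.3801 progress per interval. Two scans precede month 3, so scan-dated PFS is 0.6199² = 0.384.

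**Step 2: share censored.** The chance that the next scan is done is q = exp(-1.380 d). The share eventually censored is (1 - q) / (1 - 0.6199 q).
- d = 5%: q = 0.9333; share = 0.0667 / 0.4214 = 16%.
- d = 10%: q = 0.8711; share = 0.1289 / 0.4600 = 28%.

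**Step 3: censoring at the last scan, or at a contact within 1.38 months of it.** The patient leaves the risk set before the missed scan date. Each scan contributes a factor of 0.6199, and the estimate is 0.384. There is no bias.

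**Step 4: contact 2 months after the last scan.** The patient is still counted at the missed scan (2.0 > 1.38) and leaves before the following one (2.0 < 2.76). The factor per scan becomes 1 - 0.3801 q.
- d = 5%: (1 - 0.3548)² = 0.6452² = 0.416, which is 3.2 points too high.
- d = 10%: (1 - 0.3311)² = 0.6689² = 0.447, which is 6.3 points too high.

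A simulation of the same set-up agrees with these values.

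**Step 5: hazard ratio.** This was simulated separately with 459 patients, a true hazard ratio of 1, median 2.0 months in both arms and 300 runs per scenario. Contact continued for a uniform 0-1 or 0-3 months after scanning stopped.

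| Scanning stops per month, A / B | HR, last-scan rule | HR, contact 0-1 month on | HR, contact 0-3 months on |
|---|---|---|---|
| 5% / 5% | 1.00-1.01 | 1.01 | 1.00 |
| 15% / 15% | 1.00-1.01 | 1.01 | 1.00 |
| 15% / 5% | 1.00-1.01 | 0.95 | 0.87 |
| 5% / 15% | 1.00 | 1.05 | 1.17 |
| 30% / 5% (extreme) | 1.00-1.01 | 0.88 | 0.69 |

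Equal loss of scans leaves the hazard ratio near 1 and only lengthens the medians. At 15% per month in both arms, the median goes from 2.76 to about 2.8 (0-1 month) or 3.1 (0-3 months). Unequal loss moves the hazard ratio in whichever direction the imbalance points.

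**The case against.** The strongest reply is that the phrase already means an assessed follow-up. Before progression, follow-up consists of clinical and radiological assessment every six weeks (Protocol 7.7, SAP 4). In SAP 4 and the flow-chart notes, the survival-only schedule starts after progression, when the patient already has a PFS event. The contact must also be one that shows no progression. On that reading most of the problem disappears. This is a fair reading, but the text does not state it. It would leave the contact clause with almost nothing to add to the last tumour assessment, and Protocol 7.7 does list survival information in addition to the scans. Two programmers could derive different dates.

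Three stronger readings are tempting and are not supported.

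- **Progression cannot be detected without imaging.** Protocol 8.1.2.1 accepts caliper measurement at physical examination, and Protocol 5.4 provides for progression documented before the first scheduled evaluation. A clinic visit can therefore reveal progression; a telephone call cannot measure a lesion. The defect is that no assessment is required at the contact.
- **PA11 makes the rule more damaging.** Stopping follow-up at once raises the number censored, but it also ends later contact. A patient scanned on schedule is cut off less than six weeks after a scan, and the flow chart schedules imaging at end of treatment. These patients fall in the no-effect case of Step 3.
- **The log-rank test and hazard ratio are biased.** That needs missed scans to differ by arm. Open-label treatment with different regimens makes this conceivable, but the documents give no rates and no direction.

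It also stands that superiority is judged on overall survival alone (SAP 10.1). For the two duration endpoints, the SAP already warns about extra censoring and censors at new therapy.

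**Conclusion.** The concern holds in a conditional form. As written, the rule permits unassessed time to count as progression-free, and it does so only when contact continues past a scheduled scan that was not done. PFS can be overstated; the documents do not show that it is.

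Under the assumptions above, the overstatement at 3 months is about 3 to 6 points, and it is zero when contact stays within one scan interval. The share censored and the two-month gap are chosen for illustration, and a uniform two-month gap means that every censored patient missed a scheduled scan. The finding that last-scan censoring is essentially unbiased rests on scans being missed independently of progression. If failing patients skip scans, neither rule is free of bias.

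The consequences are limited because PFS is secondary and descriptive and overall survival is untouched. The change is still worth making. The single PFS analysis in SAP 10.4.1 has no sensitivity analysis beside it, and SAP 4.2.1 lacks the caution about extra censoring that SAP 4.2.4 to 4.2.7 carry.

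**What to change.** In SAP 4.2.1, 4.2.4 and 4.2.5, censor at the date of the last tumour assessment showing no progression; for PFS, use the randomisation date if there is no such assessment. Keep the existing new-therapy censoring in 4.2.4 and 4.2.5. Align Protocol 11.4, or record the difference in the SAP.

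Keep the present rule as a sensitivity analysis. It would also help to report by arm the time from last tumour assessment to last contact in censored patients, which shows directly whether the choice matters, and to add the PA11 censoring caution to 4.2.1.

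The cost is a wording change and one derivation. No new data are needed, since tumour assessments are already listed under 16.2.6 in SAP Appendix 1. The downside is that some censored times become slightly shorter.
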